#### Indeterminate:

- The Clinical Response to test article could not be adequately inferred due to:
  - a. Subjects were not seen for EOT evaluation because they withdrew consent or were lost to follow-up.
  - b. Other specified reason.

#### 8.13.1.3 Investigator's Assessment of Clinical Response at PTE

The PTE assessment is to be performed 5 to 10 days after the subject's last day of therapy. The investigator will determine which of the following clinical outcomes the subject meets based on the criteria below (must select 1 outcome):

#### Clinical Success:

- Survival after completion of a test article regimen without receiving any systemic antibacterial therapy other than test article;
- Resolution of signs and symptoms of the infection present at Screening with no new symptoms or complications attributable to CABP; and
- No need for further antibacterial therapy.

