#### Clinical Success:

- The subject is alive and the infection is sufficiently resolved such that further antibacterial therapy is not needed.
  - These subjects may have some residual findings related to infection (ie, cough) requiring ancillary (ie, non-antibiotic) treatment (eg, expectorant).
- In order for the subject to be considered a Clinical Success at EOT, the subject may not meet any criteria for Clinical Failure or Indeterminate at EOT.

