#### Clinical Failure:

- The subject requires alternative antibacterial treatment for CABP prior to PTE related to either:
  - a. Progression or development of new symptoms of CABP or
  - b. Development of infectious complications of CABP (eg, empyema, lung abscess).
- Other reasons for Clinical Failure are:
  - c. The subject is receiving antibiotics that may be effective for the infection under study for a different infection from the one under study.
  - d. Death prior to PTE.

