#### Indeterminate:

- The clinical response to test article could not be adequately inferred due to:
  - a. Subjects were not seen for PTE evaluation because they withdrew consent or were lost to follow-up.
  - b. Other specified reason.

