5.2.2.2 Estimand Framework for Investigators Assessment of Clinical Response

	Investigators Assessment of Clinical Response	
Population	ITT and CE-PTE Populations	
Variable/Endpoint	Investigator Assessment of Clinical Success	
Handling of intercurrent	Composite estimand as the following ICE's are	
events	incorporated into the variable/endpoint:	
	• Receipt of alternative (rescue) therapy (failure)	

The four attributes of estimand are described below:

	 Receipt of antibiotic that may be effective for CABP for a different infection (failure) Death (failure) 	
Population-level summary	Difference between treatment groups in percentage of subjects with an investigators assessment clinical sucess	

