6.1.4.3 Concomitant Antibiotic Therapy

Subjects who receive any systemic concomitant antibiotic therapy from the time of the first dose of test article through the time of the last dose of test article at EOT and through the PTE Visit with a spectrum of activity against the known or potential infecting pathogen(s) responsible for the CABP under study will be excluded from the CE-EOT and CE-PTE populations, respectively, unless the subject receives the antibiotic therapy for treatment of the CABP due to insufficient therapeutic effect of the test article (ie, for progression or development of new symptoms of CABP or development of infectious complications of CABP).

Subjects who receive a systemic concomitant antibiotic that is not effective against the baseline pathogen, or if no pathogen is isolated, and the antibiotic does not have activity against CABP pathogens, will be included in the CE-EOT and CE-PTE populations.

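### The PTE Clinical Success and Clinical Failure definitions leave two groups of observed subjects in neither, so as written they fall to Indeterminate and leave CE-PTE

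*Protocol*

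**What the plan says.** Protocol 8.13.1.3 makes the investigator choose one PTE outcome: "The investigator will determine which of the following clinical outcomes the subject meets based on the criteria below (must select 1 outcome".

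- **Success** has three joint conditions. The first is "Survival after completion of a test article regimen without receiving any systemic antibacterial therapy other than test article". The second is "Resolution of signs and symptoms of the infection present at Screening with no new symptoms or complications attributable to CABP; and". The third is that no further antibacterial therapy is needed. SAP 5.2.2.1 repeats all three.
- **Failure** covers alternative antibacterial treatment for CABP because of progression, new symptoms or infectious complications; death before PTE; and this case: "The subject is receiving antibiotics that may be effective for the infection under study for a different infection from the one under study". SAP 5.2.2.1 repeats the list. The estimand in SAP 5.2.2.2 names the same antibiotic event: "Receipt of antibiotic that may be effective for CABP for a different infection (failure".
- **Indeterminate** opens with "The clinical response to test article could not be adequately inferred due to". It then lists subjects who were not seen, and an open-ended other reason. SAP 7.3 applies it when the investigator cannot decide between Success and Failure, or when the response is missing.

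Three other places bear on this:

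- EOT Success (Protocol 8.13.1.2) carries an allowance that the PTE list lacks: "These subjects may have some residual findings related to infection (ie, cough) requiring ancillary (ie, non-antibiotic) treatment".
- The protocol synopsis asks for resolution at PTE only as far as makes more antibacterial treatment unnecessary, and states no bar on other antibacterials.
- SAP 6.1.4.3 says that CE-EOT and CE-PTE will include "Subjects who receive a systemic concomitant antibiotic that is not effective against the baseline pathogen", and likewise, where no pathogen is isolated, subjects whose antibiotic lacks activity against CABP pathogens.

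**The concern.** Success excludes every non-study systemic antibacterial, while Failure counts only those that might work against CABP. Success requires resolution, but lack of resolution alone is not a Failure criterion. The two definitions therefore do not meet in the middle.

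PTE response is the EMA primary endpoint, and non-inferiority must be shown in both ITT and CE (Protocol 12.6.2 and 12.6.3). Protocol 12.6.2 allows only Success and Failure in CE. If a subject with a known course is recorded as Indeterminate, the category chosen decides whether that subject is in the CE analysis. For group (b) the subject is dropped because of how he or she responded, so CE membership depends on outcome. Sites could also differ: one may follow the looser synopsis wording and record Success, another may follow 8.13.1.3 and record Indeterminate.

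**Working it through.** **Classifying the two groups from the text**

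| Test | (a) Recovered, inactive antibacterial for another infection | (b) Incomplete resolution, no progression, no antibacterial need |
|---|---|---|
| Success: no non-study systemic antibacterial | not met | met |
| Success: resolution | met | not met |
| Failure: rescue for CABP | no | no |
| Failure: potentially effective antibiotic for another infection | no | no |
| Failure: death | no | no |
| Result | neither | neither |

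Group (a) can occur. Protocol 7.13 restricts only antibacterials with potential CABP activity, and only through EOT; 7.14 permits whatever is not prohibited; and SAP 6.1.4.3 writes a rule for such subjects. Group (b) can be Success at EOT and then lose that status at PTE without getting worse.

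The remaining category is Indeterminate, other reason. In SAP Table 4, EOT Success with PTE Indeterminate gives Indeterminate overall. SAP 6.1.4.5 then excludes the subject from CE-PTE. In ITT the subject stays in the denominator as a non-success, exactly as a Failure would.

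**Reproducing the planned power**

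The inputs are a margin of 10%, one-sided alpha 0.025 and 1:1 allocation. ITT has 335 per arm at 85%. CE has 268 per arm at 89% (SAP 5.1.1 and Protocol Table 4). The running text of Protocol 12.2 prints 80% for CE, which would give 82.0%, so 89% is used.

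The Farrington-Manning power is Φ{[Δ√n − 1.96·σ0]/σ1}, where σ1 = √[2p(1−p)] and σ0 uses the two rates fitted under a difference of −10%.

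- ITT: constrained rates 0.7874 and 0.8874, σ0 = 0.5171, σ1 = 0.5050. Power = Φ(1.618) = 94.7%, as stated.
- CE: constrained rates 0.8228 and 0.9228, σ0 = 0.4658, σ1 = 0.4425. Power = Φ(1.636) = 94.9%, as stated.

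**Illustration only: equal shares in both arms**

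Assume that a share x of the 670 ITT subjects is affected, that all are otherwise evaluable, and that all are counted as successes in the planned rates. Planned CE successes are 0.89 × 536 = 477.04.

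- Dropped: N = 536 − 670x, rate = (477.04 − 670x)/N.
- Kept as Failure: N = 536, rate = (477.04 − 670x)/536.

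| x | Subjects | CE if dropped: N, rate, power | CE if kept as Failure: rate, power |
|---|---|---|---|
| 1% | 6.7 | 529.3, 88.86%, 94.5% | 87.75%, 93.2% |
| 3% | 20.1 | 515.9, 88.57%, 93.5% | 85.25%, 89.5% |
| 5% | 33.5 | 502.5, 88.27%, 92.4% | 82.75%, 85.9% |

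If the same shares are non-successes in ITT (rates 84%, 82%, 80%), power is 93.7%, 91.7% and 89.6%. This measures how strict the Success wording is, not the gap, because Failure and Indeterminate count alike there.

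**Illustration only: unequal shares**

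Assume 3% of 335 (10.05 subjects) on omadacycline, 1% (3.35) on moxifloxacin, and a true CE rate of 89% in both arms (238.52 successes of 268).

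- Recorded Success: difference 0.0 points.
- Dropped: 228.47/257.95 − 235.17/264.65 = 88.57% − 88.86% = −0.3 points.
- Failure: 228.47/268 − 235.17/268 = 85.25% − 87.75% = −2.5 points. This label is plausible for group (b) only.

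Reversing the shares reverses the sign.

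**The case against.** **A category does exist.** A reader might infer that these subjects cannot be classified at all. The documents do not support that. The other-reason line under Indeterminate is open-ended, and SAP 7.3 can be read to cover anyone who is neither Success nor Failure. This stands. What remains is that the category is meant for responses that cannot be inferred, and these can be.

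**ITT is determinate.** Read literally, both groups are non-successes whichever label is used. This stands. The ITT rate moves only if a site records Success against the wording of 8.13.1.3.

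**The CE rules need not contradict each other.** SAP 6.1.4.3 may mean only that such subjects are not excluded on antibiotic grounds, with 6.1.4.5 still applying. That reading is available, so a flat contradiction is not established. The practical result is still that a recovered group (a) subject, whom 6.1.4.3 says will be included, is removed.

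**The EMA rules are not in hand.** The CE criteria and Table 4 come from a SAP in which PTE is descriptive (9.3). SAP 3 announces a separate EMA SAP, which was not supplied and might resolve this. Protocol 12.6.2 shows only that CE uses Success and Failure.

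**Safeguards exist.** The trial is double-blind. Evaluability review is blinded and precedes database lock, apart from criteria that need the actual treatment (SAP 6.2). Reasons for Indeterminate are summarized by arm (SAP 9.3). These limit bias but do not supply the missing rule.

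**A strict bar can be deliberate.** Failing to credit anyone who took another antibacterial is a defensible conservative choice. It does not explain why the Failure list and the estimand are narrower.

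**Conclusion.** The gap holds on the text. Two kinds of observed subject meet neither PTE definition and, as written, go to Indeterminate: a non-success in ITT and an exclusion from CE-PTE. For group (b) this makes CE membership depend on outcome. For group (a) it defeats the apparent purpose of SAP 6.1.4.3.

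The reach is limited to the EMA primary, subject to an EMA SAP not seen, and a descriptive FDA secondary. The FDA primary, early clinical response, is untouched.

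A reader might infer from the power and difference figures that the EMA analysis is materially biased or underpowered. The documents do not support that. The affected share, and any imbalance between arms, are assumptions. The figures also suppose that these subjects are successes in the planned rates. The PTE definition behind the CABP-1200 rates is not shown, and if it was similar the loss would be counted twice. Severity is minor to moderate.

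**What to change.** Make these changes before unblinding, in the protocol and in both SAPs:

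1. For the derivation of the PTE endpoint, limit the antibacterial bar in Success (Protocol 8.13.1.3, SAP 5.2.2.1) to therapy potentially effective against CABP. This matches the Failure list, the estimand and SAP 6.1.4.3. It changes classification only, not which treatments are permitted.
2. Reconcile the resolution wording in the synopsis, EOT Success and PTE Success. Do not let observed subjects with incomplete resolution and no antibacterial need default to Indeterminate. If the resolution condition in 8.13.1.3 is kept, they are non-success, recorded as Failure, and stay in CE-PTE.
3. Reserve Indeterminate for responses that truly cannot be inferred.

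The cost is a written amendment with the approvals in Protocol 13.6.2, a note to sites and some blinded queries. Step 2 gives up some CE power, as the kept-as-Failure column shows under its assumptions.

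There are two data limits. The through-PTE antibacterial summary in SAP 12.2 covers only CE-PTE, so it would omit subjects dropped as Indeterminate. Symptom severity is scored at PTE, but the schedule as it reads here shows no physical examination or vital signs at that visit, so symptom scores alone cannot confirm resolution of signs.

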#### Clinical Failure:

- The subject requires alternative antibacterial treatment for CABP prior to PTE related to either:
  - a. Progression or development of new symptoms of CABP or
  - b. Development of infectious complications of CABP (eg, empyema, lung abscess).
- Other reasons for Clinical Failure are:
  - c. The subject is receiving antibiotics that may be effective for the infection under study for a different infection from the one under study.
  - d. Death prior to PTE.

#### Indeterminate:

- The clinical response to test article could not be adequately inferred due to:
  - a. Subjects were not seen for PTE evaluation because they withdrew consent or were lost to follow-up.
  - b. Other specified reason.

### 8.13.2 Clinical Stability

The formal determination of the subject's Clinical Stability will be done programmatically using the investigator's assessment of the subject's vital signs entered into the eCRF. The investigator is not responsible for categorizing the subject's Clinical Stability. Clinical Stability will be assessed daily and analyzed by day, ECR window, EOT, and PTE.

Patients will be considered clinically stable if they achieved all of the following criteria:

- Temperature  $\leq 37.8^{\circ}C (100^{\circ}F);$
- Heart Rate  $\leq 100$  beats/minute;
- $RR \le 24$  breaths/minute;
- SBP  $\geq$  90 mmHg; and
- Arterial Oxygen Saturation  $\ge 90\%$  or  $PaO_2 \ge 60$  mmHg on room air.

### 8.14 Microbiologic Response

#### 8.14.1 Respiratory Culture and Gram Stain

At the Screening visit collection of an adequate quality expectorated or induced sputum or other respiratory specimen reflecting fluid from the lower respiratory tract (eg, respiratory fluid obtained by bronchoalveolar lavage or bronchoscopy; pleural fluid obtained by thoracentesis; or expectorated or induced sputum meeting adequacy criteria) should be attempted from all subjects and submitted to the local microbiology laboratory for Gram stain and culture (see Appendix 1). The date, time and type of specimen submitted will be recorded on source documents at the local laboratory. These specimens may be obtained as part of routine, non-study evaluation of a subject being evaluated for CABP and therefore could be obtained prior to obtaining informed consent.

An adequate quality sputum specimen will be defined as having the following 2 findings as reported by the local laboratory:

- 1. < 10 Squamous epithelial cells/low power field (LPF) (ie,  $100 \times$ )
- 2. > 25 Polymorphonuclear cells/LPF (ie,  $100 \times$ )

Adequate quality sputum specimens and other Screening respiratory specimens for culture should be obtained prior to first dose of test article. In the event that a sputum specimen is determined to be inadequate or cannot be obtained prior to the first dose of test article, collection of a specimen should be attempted within 24 hours after the first dose of test article. As the infection responds to therapy, obtaining repeated specimens for culture or examination may not be clinically appropriate and/or there may be no material for culture. At the EOT and/or PTE visit, respiratory specimen cultures and Gram stains should be obtained only for subjects who are Clinical Failures and require alternative antibacterial treatment for CABP.

All respiratory and blood specimens submitted to the local laboratory are to be processed for a Gram stain of the specimen and for aerobic culture. Laboratory reports on Gram stains should include a semi-quantitative description of the number of polymorphonuclear leukocytes per LPF (ie,  $100\times$ ) and a description of bacteria seen. For Gram stains of respiratory specimens, a semi-quantitative description of the number of squamous epithelial cells per LPF (ie,  $100\times$ ) should also be included. Culture results are to include identification of all pathogens to the level of genus and species. Susceptibility testing for moxifloxacin (or other fluoroquinolones) can be performed locally using a standard method chosen by the laboratory. Results of this testing can be used by investigators along with clinical findings to help guide therapy.

All isolates identified by the local laboratory from expectorated or induced sputum specimens meeting the 2 criteria that define the specimen as being of adequate quality and/or that are isolated from respiratory specimens or blood and are potential pathogens as defined in the Local/Regional Clinical Microbiology Laboratory Manual, will be submitted to the Central Laboratory for verification of genus and species and for standardized minimum inhibitory concentration (MIC) testing performed for omadacycline, moxifloxacin and a panel of currently approved antibiotics. In the event that local laboratory genus and species identification are not consistent with Central Laboratory results, a back-up isolate should be sent to the Central Laboratory.

Details concerning Gram stains and cultures will be provided in the Local/Regional Clinical Microbiology Laboratory Manual.

# 8.14.2 Urine for Legionella pneumophila and Streptococcus pneumoniae Antigen Screening

At the Screening visit, urine will be collected to test for the presence of *Legionella pneumophila*, and *Streptococcus pneumoniae* antigens. Testing will be performed at the local laboratory using kits supplied by the sponsor and the results will be recorded on the eCRF.

# 8.14.3 Serology for Legionella pneumophila, Mycoplasma pneumoniae, and Chlamydophila pneumoniae Titers

At the Screening visit, and at the PTE visit, blood samples will be collected to conduct serology for *Legionella pneumophila*, *Mycoplasma pneumoniae* and *Chlamydophila pneumoniae* by the Central Laboratory.

# 8.15 Pharmacokinetic Assessments

Instructions will be provided to sites with detailed information on sample collection, handling, and shipment requirements. All samples will be given a unique identifier. The exact clock time of dosing, date and time of last food intake, as well as actual sample collection date and time will be entered on the eCRF.

#### 8.16 Adverse Events

An AE is any untoward, undesired, or unplanned event in the form of signs, symptoms, disease, or laboratory or physiologic observations occurring in a person given a test article or in a clinical study. The event does not need to be causally related to the test article or clinical study. An AE includes, but is not limited to, the following:

- Any clinically significant worsening of a preexisting condition.
- An AE occurring from overdose of a test article, whether accidental or intentional. Overdose is a dose greater than that specified in the protocol.
- An AE occurring from abuse (eg, use for nonclinical reasons) of a test article.
- An AE that has been associated with the discontinuation of the use of a test article.

#### 8.17 Serious Adverse Events

A serious adverse event (SAE) is an AE that:

- Results in death.
- Is life-threatening (see below)
- Requires hospitalization or prolongation of an existing hospitalization (see below).
- Results in a persistent or significant disability or incapacity (see below).
- Results in a congenital anomaly or birth defect.
- Additionally, important medical events that may not result in death, be life-threatening, or require hospitalization may be considered SAEs when, based on appropriate medical judgment, they may jeopardize the subject and may require medical or surgical intervention to prevent any one of the outcomes listed above in this definition. Examples of such events include allergic bronchospasm requiring intensive treatment in an emergency room or at home, blood dyscrasias or convulsions that do not result in hospitalization, or development of drug dependency or drug abuse.

Life-threatening refers to immediate risk of death as the event occurred per the reporter. A lifethreatening experience does not include an experience that, had it occurred in a more severe form, might have caused death, but as it actually occurred, did not create an immediate risk of death. For example, hepatitis that resolved without evidence of hepatic failure would not be considered life-threatening, even though hepatitis of a more severe nature can be fatal. Similarly, an allergic reaction resulting in angioedema of the face would not be life-threatening, even though angioedema of the larynx, allergic bronchospasm, or anaphylaxis can be fatal.

Hospitalization is official admission to a hospital. Hospitalization or prolongation of a hospitalization constitutes criteria for an AE to be serious; however, it is not in itself considered an SAE. In absence of an AE, a hospitalization or prolongation of a hospitalization should not be reported as an SAE by the participating investigator. This is the case in the following situations:

- The hospitalization or prolongation of hospitalization is needed for a procedure required by the protocol
- The hospitalization or prolongation of hospitalization is part of a routine procedure followed by the center (eg, stent removal after surgery). This should be recorded in the study file.
- A hospitalization for a preexisting condition that has not worsened

Disability is defined as a substantial disruption in a person's ability to conduct normal life functions.

If there is any doubt about whether the information constitutes an SAE, the information is treated as an SAE.

### 8.18 Other Reportable Information

Certain information, although not considered an SAE, must be recorded, reported, and followed up as indicated for an SAE. This includes:

- Pregnancy exposure to a test article: If a pregnancy is confirmed, use of the test article must be discontinued immediately. Information about pregnancy exposure includes the entire course of pregnancy and delivery, and perinatal and neonatal outcomes, even if there are no abnormal findings. Both maternal and paternal exposures are considered other reportable information. For exposure involving the female partner of a male subject, the necessary information must be collected from the subject, while respecting the confidentiality of the partner.
- Lactation exposure to a test article with or without an AE.
- Overdose of a test article as specified in this protocol with or without an AE.
- Inadvertent or accidental exposure to a test article with or without an AE.

